#### 4.8.1 Procedures for Emergency Disclosure of Allocation Numbers

- (1) In the event the conditions described above for disclosure of allocation numbers are deemed met, the investigator (attending physician) shall take actions according to one of the two procedures below.
- (2) Procedure 1: The investigator (attending physician) shall unseal the envelope marked "Procedure for Emergency Code Breaking of Allocation Numbers" that has been prepared in advance by the head of the independent data monitoring board and sealed and distributed by the secretariat, and follow the instructions provided therein.
- (3) Procedure 2: The investigator (attending physician) shall contact the secretariat by phone and follow the procedures as instructed.
- (4) When contacted by the investigator (attending physician) per Procedure 2, if the secretariat alone is unable to take actions in response, he/she shall promptly contact the allocation manager to confirm the study drug group and contact the investigator (attending physician) by phone or email.

#### 4.9 Baseline Survey and Study Treatment Commencement

The investigator (attending physician) shall present information to the patient, obtain informed consent, and carry out baseline observations and assessments immediately after completing the patient's enrollment. After contacting the secretariat by email, commence the study treatment on the morning of the next day (Day 1) after the baseline survey (Day 0).

In the event the study treatment cannot be commenced as a participant is found to be ineligible after his/her enrollment or cannot participate for some other reason, discontinue the study for the participant, record the reason for doing so on the case report form (CRF), and contact the secretariat promptly by email or phone.

#### 4.10 Study Treatment

##### 4.10.1 Definition of Study Treatment

The study treatment is defined as the randomly allocated treatment as described for the two groups below.

- (1) Steroid group

Administer orally a steroid (2 mg of betamethasone tablets 0.5 mg "SAWAI" twice daily in the

morning and noon) for one week (until Day 7).

(2) Placebo group

Administer orally placebo capsules (twice daily in the morning and noon) for one week (until Day 7).

#### 4.10.2 Administration of Study Treatment

- (1) The investigator (attending physician) shall administer the study treatment prepared as allocated starting from the day following enrollment (Day 1).
- (2) Dispense the study drug without changing the order of packaging.
- (3) The study drug is provided to outpatient participants by the investigator (attending physician) and to inpatient participants by the investigator (attending physician) or a clinician instructed by the investigator (attending physician).

#### 4.10.3 Study Drugs

- (1) In the present trial, patients in the control group will be treated with placebo. Thus, prepare capsules by filling JP-conforming capsules with betamethasone drug product and lactose, and prepare placebo in a similar manner by filling the capsules with lactose alone.
- (2) An opinion issued on January 7, 2013 by officials of the Compliance and Narcotics Division, Pharmaceutical and Food Safety Bureau, Ministry of Health, Labour and Welfare on the preparation of the study drug for the present trial indicated that this protocol does not violate the Pharmaceutical Affairs Law.
- (3) A study drug manager appointed by the allocation manager shall prepare and label the study drug according to the allocation schedule generated by the allocation manager in a formulation room that meets class 10,000 clean room standards.
- (4) The packaging form of the study drug is as follows. Dispense a total of 14 doses (for 7 days), with each dose wrapped in a piece of powder wrapping paper and labeled with the allocation number on the exterior. Place the required number of packets for one participant into an aluminum zipper bag containing a desiccant to remove moisture. Place security tape over the opening of the zipper bag to allow identification of any bags that have been opened.

#### 4.10.4 Investigational Product (steroid)

Capsules containing a 2-mg betamethasone tablet, a synthetic adrenocortical hormone, per capsule

Nonproprietary name: Betamethasone

Chemical name: 9-Fluoro-11 $\beta$ ,17,21-trihydroxy-16 $\beta$ -methylpregna-1,4-diene-3,20-dione

See the package insert of Betamethasone Tablets (Appendix) for details. Always obtain the latest version of the package insert to verify information.

#### 4.10.5 Control Drug (placebo)

Capsules containing lactose that are superficially indistinguishable from the investigational product

#### 4.10.6 Method of Study Drug Administration

- (1) Administer orally one capsule twice daily, morning and noon.
- (2) There shall be no dose increase or reduction during study treatment.
- (3) In the event the treatment is interrupted (dose interruption) after study commencement, continue to carry out the study and perform assessments as specified. The term “interruption” in the present trial means an interruption (dose interruption) of the study treatment for some unspecified reason followed by treatment resumption.
- (4) In the event the administration of the study drug is discontinued after study commencement, perform assessments promptly after discontinuation of the study treatment. The term “study treatment discontinuation” in this study means discontinuation of the study treatment followed by no resumption of the study treatment.
- (5) Survey the drug compliance status by asking the participants to mark a verification check box on the dosing diary (Appendix) each time the participant takes a dose during the study treatment period.
- (6) Instruct the participants to always drink water before taking a capsule.
- (7) In cases where there is leftover study drug after the study treatment, check the dosing diary and collect any leftover study drug.

#### 4.10.7 Study Drug Management

- (1) The study drug manager shall create a standard operating procedure to ensure quality control is maintained in the conduct of the study and establish a standard operating procedure for study drug management.
- (2) Document distribution, storage, control, and collection of the study drug each time the study drug is transferred or delivered/received.
- (3) The study drugs shall be managed as directed in the standard operating procedure to ensure quality control is maintained in the conduct of the study.

#### 4.11 Concomitant Therapies

##### 4.11.1 Administration and Documentation of Concomitant Therapies

- (1) During the study period, follow the provisions provided below under “Prohibited Concomitant Therapies.”
- (2) Treat adverse events appropriately, at the discretion of the investigator (attending physician) at the study site where the event occurred.
- (3) Survey and document any concomitant therapies administered between eligibility verification and study treatment completion or discontinuation.

##### 4.11.2 Prohibited Concomitant Therapies

During the study period, the administration for the first time of any of the medications or therapies described below is prohibited. In cases where a prohibited concomitant therapy cannot be discontinued

or must continue, withdraw the participant concerned from the study.

- (1) Oral or injectable adrenocortical hormone preparations other than the therapeutic agent used in the study
- (2) Oral administration of a synthetic corpus luteum hormone preparation
- (3) Surgery
- (4) Radiation therapy (except radiation therapy to alleviate symptoms)
- (5) Chemotherapy

[Rationales]

- (1), (2) Such hormone preparations can affect efficacy evaluations
- (3) Postoperative healing of surgical wounds is affected
- (4), (5) Decreased white blood cell count affects susceptibility to infections

#### 4.12 Study Treatment Discontinuation

##### 4.12.1 Study Treatment Discontinuation and Study Discontinuation

The investigator (attending physician) shall promptly discontinue the study treatment in a participant if any of the following apply after his/her enrollment and discontinue the study in the participant.

- (1) When the investigator (attending physician) concludes that a participant is unable to continue the study treatment due to the occurrence of an adverse event
- (2) When a participant must receive a prohibited concomitant therapy
- (3) When a participant expresses the wish to discontinue the study treatment or to discontinue or withdraw consent for study participation
- (4) When a participant is found to be ineligible after his/her enrollment
- (5) When the independent enrollment supervisory board requests a discontinuation
- (6) When a participant stops making office visits after relocation or transferring to another hospital
- (7) When a blood test other than those scheduled during the trial period is required
- (8) When a participant is deemed by the investigator (attending physician) as unable to continue the study due to a reason other than those described in items (1) through (7) above

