##### 4.12.2 Data Related to Study Treatment Discontinuation

Perform observations, tests, and assessments required at discontinuation as soon as possible. If 3 days' worth of data before study treatment discontinuation are available, such data may be used as the data at study treatment discontinuation.

Record the reason for discontinuing study treatment on the CRF.

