## Observations, Tests, Assessments

## 4.15 Information Subject to Reporting Requirement during Study/Observation Period and Reporting Schedule

Item	Time	At Eligibility Verification	Enrollment Allocation	Baseline	During Study Treatment						Study Treatment Discontinuation or Completion (Day 7)	Outcome Survey
					1	2	3	4	5	6		
Day		0	0	0	1	2	3	4	5	6		
Inclusion/exclusion criteria verification												
Approval from the independent enrollment supervisory board												
Consent acquisition												
Patient characteristics: sex, date of birth or age, name of the diagnosed primary cancer												
Allocation (study drug) number												
Body height and weight 												
Study drug compliance												
Administration of concomitant therapies												
ECOG PS												
QOL assessment												
NRS												
Blood tests: CRP, white blood cell count, hemoglobin, platelet count, blood glucose test date				 a)							 b)	
Occurrence of adverse event					→							
If discontinued: date of and reason for discontinuation												
Outcome survey: date of death or verification of final outcome, reason for ending trial												

a) Data obtained within the two weeks immediately prior to Day 0 may be referenced.

b) Data obtained within one week from Day 7 may be referenced.

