#### 4.16 Information on Survey Period

- (1) In the present trial, out of consideration for participants receiving outpatient palliative care while undergoing home care, conduct the eligibility verification, enrollment, allocation, and baseline survey on the same day (Day 0).
- (2) On the day following enrollment and the baseline survey is defined as Day 1 of the study treatment, which continues until Day 7.
- (3) Out of consideration for participants receiving outpatient palliative care while undergoing home care, the study treatment is to conclude on Day 7.
  - 1) If the next visit of an outpatient participant is postponed due to a holiday/weekend, give the participant an envelope containing a QOL questionnaire and an NRS form on Day 0 and ask the participant to fill out the forms on Day 7, place the forms in the envelope, and bring them to the next outpatient visit.
  - 2) If the next visit of an outpatient participant is postponed due to a holiday/weekend, the investigator (attending physician) is to conduct the ECOG PS survey on the outpatient

visit that is closest to Day 7.

- (4) Conduct an outcome survey on death of participants after discontinuation or completion of the study treatment.

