#### 4.17.3 Information to be Reported at Discontinuation of Study Treatment

- (1) Discontinuation of study treatment is defined as no resumption of the study drug on or before Day 7 after one or more doses of the study drug.
- (2) Upon discontinuing the study treatment, conduct the observations and tests required at discontinuation as soon as possible.
- (3) Ask patients to fill out the QOL questionnaire and NRS form.
- (4) If 3 days' worth of data before study treatment discontinuation are available, use such data as the data at study treatment discontinuation.

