## 6 Endpoints

### 6.1 Primary Endpoints

Fatigue (FA) score of EORTC QLQ-C15-PAL

The primary endpoint selected is the fatigue (FA) score, which represents a participant's QOL, on the EORTC QLQ-C15-PAL used to evaluate QOL on Day 7 after study commencement.

[Rationale for the choice of primary endpoint]

In the present trial, the subscale fatigue (FA) score as part of the assessment of patient QOL is considered the representative parameter of QOL and selected as the primary endpoint.

Palliative medicine is an approach aimed at improving QOL in patients and their families facing the issues related to a life-threatening disease. PS2/3 terminal-stage patients with advanced cancer-related fatigue who participate in the present trial share the treatment goal of QOL improvement. Thus, the QOL in participants will be assessed, with the score serving as an endpoint for assessing the efficacy of palliative medicine. The QOL questionnaire, however, is based on a multi-dimensional scale. The subscale fatigue (FA) has the greatest effect on QOL and is considered a representative parameter.

To reduce the load from EORTC on the patients receiving palliative care, the number of questions has been reduced from 30 in the EORTC QLQ-C30 used routinely to assess QOL in cancer patients to 15 in the disease-specific EORTC QLQ-C15-PAL for palliative care patients used to assess QOL in the present trial. Its Japanese version has been validated, with the validation results published. Registration with EORTC will take place before use.

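### Stopping study drug also ends fatigue data collection before Day 7, and the 3-day substitution rule does not exclude the Day 0 score

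*Protocol*

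**What the plan says.** Section 4.12.1 lists eight circumstances and instructs the investigator to stop study treatment promptly if "any of the following apply after his/her enrollment and discontinue the study in the participant". One of them is "When a participant expresses the wish to discontinue the study treatment or to discontinue or withdraw consent for study participation", so a wish to stop the drug, with consent intact, is enough. Others are an adverse event and the need for an unscheduled blood test. Section 4.11.2 likewise withdraws from the study a participant whose prohibited therapy cannot be stopped.

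For someone who stops, 4.10.6(4) says to "perform assessments promptly after discontinuation of the study treatment". The schedule in 4.15 has one column for the second QOL and NRS assessment, "Study Treatment Discontinuation or Completion (Day 7"). Section 4.17.3(3) asks for the QOL and NRS forms at that point. After that, 4.13.2 and 4.16(4) provide only for a survey of deaths.

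On substitute data for the 3 days before stopping, 4.12.2 says "such data may be used as the data at study treatment discontinuation", while 4.17.3(4) says "use such data as the data at study treatment discontinuation".

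The primary endpoint in 6.1 is the FA score from the questionnaire "used to evaluate QOL on Day 7 after study commencement". Section 7.1 tests the change in FA between arms, and 7.2 removes from the FAS anyone without the data needed for the major assessments.

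**The concern.** The endpoint is fixed at Day 7, but the protocol tells sites not to go on to Day 7 with a participant who has stopped the drug. A score taken after, say, two days of treatment answers a different question from one taken at one week. If that score is not accepted as the endpoint, 7.2 takes the participant out of the FAS. Either way the randomized comparison is weakened for a group selected after randomization. A SAP can choose how to treat a missing score, but it cannot recover a questionnaire that was never handed out.

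The 3-day rule adds a second problem. It is permissive in one section and directive in the other, it does not name the assessments it covers, and it has no stated rank against the fresh form that 4.17.3(3) requests. Because the only scheduled fatigue score before discontinuation is the baseline, applying the rule to FA could put a pre-treatment value in a post-treatment field.

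**Working it through.** **Timing.** Inputs: baseline on Day 0 and first dose on Day 1 (4.9); QOL and NRS scheduled only at baseline and at discontinuation or Day 7 (4.15); a 3-day look-back (4.12.2, 4.17.3(4)), read here as the three days before stopping. For a stop on Day d the window runs from Day d−3 to Day d−1. It contains Day 0 when d−3 ≤ 0 ≤ d−1, that is, when 1 ≤ d ≤ 3.

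- d = 1: Days −2 to 0, contains baseline.
- d = 2: Days −1 to 1, contains baseline.
- d = 3: Days 0 to 2, contains baseline.
- d = 4: Days 1 to 3, no scheduled score. The same holds for d = 5 and d = 6.

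So the only scheduled FA value the rule can supply is the baseline, and then change = FA(Day 0) − FA(Day 0) = 0.

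**The plan's own sample size, for scale (4.2).** 15.5/30.2 = 0.513 (stated 0.51). For 0.5 SD, two-sided 5% and 90% power, n per arm = 2 × (1.960 + 1.282)² / 0.5² ≈ 84.1. The stated figure is 84; rounding up gives 85, and power at 84 is 89.98%. Enrolment: 168/(1 − 0.20) = 210. These figures reproduce and are not in dispute.

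**Illustration 1: the same share f copied in both arms.** The protocol gives no share, so f is assumed, up to its 20% total dropout rate. The copied participants are assumed otherwise to have had their arm's mean change. Expected difference = 0.5 × (1 − f) SD.

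- f = 10%: 0.5 × 0.90 = 0.45 SD.
- f = 20%: 0.5 × 0.80 = 0.40 SD.

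With 105 per arm all contributing a score and the SD held fixed, power = Φ(difference × √(105/2) − 1.96). This is 95.2% at f = 0, 90.3% at 10% and 82.6% at 20%. If the SD also shrinks because of the zero changes (placebo mean change 0), power is 92.7% at 10% and 89.3% at 20%.

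**Illustration 2: copying in one arm only.** Assume a true difference of 0.5 × 30.2 = 15.1 points in favour of steroid, a placebo mean change of −10 (so steroid −25.1), and 20% copied.

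- Steroid only: 0.80 × (−25.1) − (−10) = −10.1.
- Placebo only: −25.1 − 0.80 × (−10) = −17.1.

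The apparent effect can move either way. With a placebo change of 0, copying in placebo alone leaves −15.1 and copying in steroid alone gives 0.80 × (−15.1) = −12.1.

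**The case against.** The strongest reply is that much of the harm depends on analysis rules the protocol does not state. Sections 4.12.2 and 4.17.3(4) label the value as belonging to discontinuation, never to Day 7, and 7.1 and 7.2 leave the primary analysis approach and missing data to the SAP. A shared schedule column shows when forms are collected, not that an early score is analysed as Day 7. That stands: a reader might infer that the off-time score is the Day 7 outcome, but the document does not say so.

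A reader might also infer that everyone stopping on Days 1 to 3 is scored at baseline. The text does not go that far. Section 4.17.3(3) asks for a fresh form, 4.12.2 is only permissive, and the rule may have been meant for items such as blood tests, which 4.17.1(13) forbids drawing solely for the trial.

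A third tempting inference is a bias of known direction, with adverse-event stops in the steroid arm and rescue-steroid stops in the placebo arm. The protocol offers no support. The one comparison it cites (5.5.2) found no significant difference in adverse events, 41/62 on active drug against 44/58 on placebo. Section 4.1 regards a delay of about a week before steroid treatment as no material departure from practice. Nor is there a basis for crediting someone off drug by Day 3 with the full treatment effect at Day 7.

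Finally, several dropout reasons in 4.2, such as death or inability to answer, would prevent a Day 7 form anyway. Not all follow-up ends: the death survey continues, and under 4.10.6(3) an interruption followed by resumption keeps all assessments.

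None of this answers the core point. Whatever the SAP says, the Day 7 form is not scheduled for discontinuers.

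**Conclusion.** The concern holds in two parts. First, on the plain text, a participant who stops study drug has no scheduled Day 7 FA score, even when consenting and able to answer, although the primary endpoint is set at Day 7. That participant contributes an off-time score or falls out of the FAS. Second, the two versions of the 3-day rule conflict and leave open the use of the Day 0 score as the discontinuation value for a stop on Days 1 to 3. This is a possible reading, not a certain one.

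The direction and size of any bias are not known from the document, because the number who stop, when they stop and in which arm are not given. The shrinkage from 0.5 SD to 0.45 to 0.40 SD illustrates an assumed 10% to 20% copied in both arms and is not a forecast. At 10% the power would still be about 90%. The change should be made because lost Day 7 scores cannot be recovered later, not because a serious bias has been shown.

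**What to change.** - In 4.12.1 and 4.17.3, separate stopping study drug from stopping data collection. Bring 4.10.6(4), 4.11.2 and the shared column in 4.15 into line, since otherwise they would contradict the amended text.
- Treated participants who stop the drug, have not withdrawn consent and are able to answer complete QLQ-C15-PAL and NRS on Day 7. Where a visit is not practical, use the procedure in 4.16(3), which already tells sites to "give the participant an envelope containing a QOL questionnaire and an NRS form on Day 0" for outpatients whose visit is postponed.
- Keep the discontinuation assessment as a separate record with its own date.
- Reconcile 4.12.2 with 4.17.3(4). State that the 3-day rule does not apply to FA, other QOL scores or NRS, and that a Day 0 value is never a post-baseline value.

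The cost is a short amendment, a CRF line, and one 15-item form and one NRS for patients who have stopped. How scores obtained after stopping, or after a prohibited therapy, enter the analysis remains for the SAP. The rules on when treatment stops are not changed.

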##### 4.12.2 Data Related to Study Treatment Discontinuation

Perform observations, tests, and assessments required at discontinuation as soon as possible. If 3 days' worth of data before study treatment discontinuation are available, such data may be used as the data at study treatment discontinuation.

Record the reason for discontinuing study treatment on the CRF.

#### 4.13 Completion of Study

##### 4.13.1 Study Completion and Assessments

The investigator (attending physician), after performing the study treatment in a patient for one week

starting from the day of commencement, shall conclude the study treatment and complete the study in the participant.

On the day of study completion (Day 7), perform the observations, tests, and assessments required at study completion.

#### 4.13.2 Outcome Survey after Study Completion

After study completion, conduct an outcome survey on deaths of participants.

#### 4.14 Completion of Study in All Participants

After the study is completed in all participants, the principal investigator shall declare a data lock according to the procedures below and then perform unblinding.

- (1) After completion of the trial in all participants, the data center shall send a notice of data-check completion to the principal investigator.
- (2) The principal investigator, after verifying the notice of completion, shall sign and date the data lock declaration (under 10.4 below).
- (3) The allocation manager, after verifying the data lock declaration issued by the principal investigator, shall disclose the allocation numbers.
- (4) There is no potential for data obtained in the present trial to be used for other purposes.

